### *Study Protocol*

The study will be conducted by [name] and his team at the Mayo Clinic. Following an initial home visit to consent the subject and ensure that all study inclusion and exclusion criteria are met, an individual appointment will be scheduled for each subject at the Mayo Clinic. The subjects will meet the health coach, receive training on using the system, and will perform one initial exercise session to ensure safety and cognitive acceptance of the intervention. The training on how to use the system will be conducted by the health coach and will include demonstration, practice, and written materials for subjects to take home. During this initial session at the Mayo Clinic each subject will also provide demographic data and complete a Chronic Respiratory Disease Questionnaire (CRDQ). For the eight week **intervention** period each subject will receive weekly health coaching plus activity monitoring. The health coaching is described below. For the activity monitoring each subject will be asked to wear the ankle and wrist monitor for the entire day, excluding bathing. Each subject will also be asked to wear a fingertip pulse oximeter while completing an exercise routine. Patients will be asked to perform the exercise routine six days a week, including at least a 5 minute walk and walking a total of 15 to 20 minutes during the day for the sole purpose of rehabilitation. The exercise routine will be the same as phase I and each participant will be provided a DVD to follow. Each participant will also have a docking station with a tablet computer. The tablet will prompt the participant daily to answer a brief series of questions on their well-being at the time of taking off the monitors at the end of the day for charging. The subject's daily steps will be available on the wrist monitor and the tablet computer. The tablet will also provide a simplified version of the report that goes to the health coach, including trend and detail data on the subject's daily activity and physiological measures.

During the eight week **control** period no health coaching will be provided or exercise prescription requested. Participants will not receive any information on their activity nor will they be asked to complete the well-being questions. During the last week of the control period all participants will be asked to wear the SenseWear Pro Armband for four days to collect data on their daily steps.

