During week 9 all participants (half of whom will be in the intervention period and half in the control period) will be asked to repeat the CRDQ via telephone. At the end of week 17 each participant will be asked to complete the CRDQ via telephone and return all of the equipment.

**Figure 10:** Diagrams showing a few representative low-dynamic exercises.

[figure not shown]

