**Sample Size**

We calculated the sample size based on our previous published data. A total sample of 104 patients (52 per group) is needed to detect a difference of 0.5 in the Chronic Respiratory Disease Questionnaire (the minimally clinical importance difference) with 80% power. See Figure 11. A sample of 104 patients is necessary to detect a difference of 1000 steps with 80% power. We plan to recruit 115 patients due to an expected attrition of 10% as seen in [name] published research in COPD rehabilitation. See Figure 12.

**Figure 11:** Diagram for power sample size for quality of life outcome

**Figure 12:** Diagram for power sample size for steps outcome

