**Analysis Plan**

The primary outcomes of the study are: change in daily steps and change in quality of life between the intervention and control conditions. Change in daily steps will be measured by comparing the mean number of daily steps in weeks 1, 9, and 17 as measured by the activity monitoring system and the SenseWear Pro Armband. Quality of life will be measured by the CRDQ, which consists of 20 items across four dimensions. A change in the score of .5 on the 7 point scale reflects a clinically significant change.

Quantitative analysis: Descriptive and inferential statistics will be used. For daily steps descriptive statistics such as means, standard deviations, medians, ranges, and frequency distributions will be examined and calculated by condition (baseline versus intervention versus control period). The mean number of daily steps of each measurement period (baseline, 9 weeks and 17 weeks in all subjects: intervention, and control) will be compared for differences. A difference of 1000 steps is considered clinically meaningful across all severities of COPD. We will also compare quality of life measured by the CRDQ (baseline versus intervention versus control period). The CRDQ data will be examined for each question, domain, and the entire instrument. We will also analyze daily steps and quality of life trajectories from weeks 1, 9, and 17 using repeated measures models. Regression equations and correlations will be performed to determine the impact of the system/coaching and adherence on outcomes adjusted by the most pertinent variables in COPD (age, dyspnea level, lung function, exacerbations and comorbidities measured by the Charlson comorbidity index).

Multivariate, repeated-measures ANOVA will be used to analyze the main pre- and postintervention effects and interactions both between and within groups. If the overall ANOVA value was significant at the  $p < .05$  level, post hoc independent-samples t tests will be conducted on the subscales of CRDQ

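### Baseline CRDQ is collected from every patient, but the post hoc subscale t tests cannot adjust for it and the regression's covariate list omits it

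*Combined protocol and SAP*

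**What the plan says.** **When the CRDQ is collected.** Under Study Protocol, each patient completes it at the initial clinic session. At week 9 all participants "will be asked to repeat the CRDQ via telephone", and at that point the sample is split: "half of whom will be in the intervention period and half in the control period". It is given again at the end of week 17.

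**How the Analysis Plan uses it.**
- Change in quality of life is one of two primary outcomes. CRDQ is compared across baseline, intervention and control, and is modelled over weeks 1, 9 and 17 with repeated measures.
- A repeated-measures ANOVA examines "main pre- and postintervention effects and interactions both between and within groups".
- If that ANOVA is significant at the 0.05 level, "post hoc independent-samples t tests will be conducted on the subscales of CRDQ".
- A regression of outcomes on the system, coaching and adherence is adjusted for "age, dyspnea level, lung function, exacerbations and comorbidities measured by the Charlson comorbidity index".

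Baseline CRDQ is not named as a covariate in any of these, or elsewhere in the documents. The plan does not say whether the t tests use final scores or change scores.

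**The concern.** At week 9 the design gives a between-group CRDQ comparison with a baseline value planned for everyone. An independent-samples t test on final scores discards that baseline. A t test on change scores subtracts it in full, which over-corrects when the correlation is below 1. ANCOVA estimates how much of the baseline to subtract, so it has lower residual variance than either at the correlations considered here.

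The regression has the same gap: five adjustment variables are named, and the baseline value of the outcome is not one of them.

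What is at stake is precision, not validity. The study is sized with little slack ("A total sample of 104 patients (52 per group) is needed to detect a difference of 0.5", at 80% power), and the unused information is already in hand.

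**Working it through.** **Inputs from the documents.** Difference 0.5, 52 per group, 80% power (Sample Size); baseline CRDQ on all patients (Study Protocol).

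**Assumptions.** Two-sided alpha of 0.05, because the sample size text gives neither alpha nor sidedness. Baseline-to-follow-up correlation r of 0.3, 0.5, 0.6 and 0.7, because the readable text gives none. Equal variance at baseline and follow-up.

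**The plan's own figure.** The figure of 104 cannot be reproduced forwards, because the readable text gives no SD. Solved backwards:
- Normal approximation: SD = 0.5 / [(1.960 + 0.842) × √(2/52)] = 0.910.
- Noncentral t: 80% power with 52 per group needs a standardised difference of 0.5547, so SD = 0.5 / 0.5547 = 0.901.

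**Variance of the group difference, relative to a single-score variance of 1.**
- Final-score t test: 1
- Change-score t test: 2(1 − r)
- ANCOVA: 1 − r²

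So ANCOVA/final = 1 − r², and ANCOVA/change = (1 − r²) / [2(1 − r)] = (1 + r)/2.

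| r | ANCOVA/final | ANCOVA/change | vs better t test | CI narrower, 1 − √ratio | 104 × ratio |
|---|---|---|---|---|---|
| 0.3 | 0.91 | 0.65 | 0.91 | 4.6% | 95 |
| 0.5 | 0.75 | 0.75 | 0.75 | 13.4% | 78 |
| 0.6 | 0.64 | 0.80 | 0.80 | 10.6% | 83 |
| 0.7 | 0.51 | 0.85 | 0.85 | 7.8% | 88 |

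These ratios need only r. They apply to any subscale and do not depend on the SD or on Figures 11 and 12.

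**Illustrative power** (52 per group, difference 0.5, noncentral t, ANCOVA on 101 degrees of freedom). It depends on which SD the implied 0.90 is:

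| r | 0.90 is a single-score SD: final / change / ANCOVA | Gain over better, points | 0.90 is a change-score SD: final / change / ANCOVA | Gain over better, points |
|---|---|---|---|---|
| 0.3 | 80.0 / 65.8 / 83.6% | 3.6 | 91.2 / 80.0 / 93.5% | 2.3 |
| 0.5 | 80.0 / 80.0 / 89.9% | 9.9 | 80.0 / 80.0 / 89.9% | 9.9 |
| 0.6 | 80.0 / 87.9 / 93.8% | 5.9 | 70.7 / 80.0 / 87.9% | 7.9 |
| 0.7 | 80.0 / 95.1 / 97.5% | 2.4 | 58.3 / 80.0 / 86.0% | 6.0 |

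A simulation of 4,000 trials per r, with 0.90 as the single-score SD, gave ANCOVA power of 83.8, 89.7, 93.2 and 97.2%, close to the formula.

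**The ANOVA that gates the t tests.** In a two-time-point repeated-measures ANOVA without a common baseline mean, the group-by-time F is the square of the change-score t. Two simulated data sets confirmed this (10.68 and 14.53 by both routes). Run that way, the gate has change-score efficiency.

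**Regression.** The variance saved is the squared partial correlation of baseline CRDQ with the outcome, given the listed covariates. At assumed values of 0.2, 0.3, 0.4 and 0.5 that is 4, 9, 16 and 25%.

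**Within-patient contrast.** The gain is the squared correlation of baseline with the difference between the two follow-up scores. With equal correlations it is 0. With correlation decaying as r, r², it is [r² − r]² / [2(1 − r)] = r²(1 − r)/2, which is 0.032, 0.063, 0.072 and 0.074.

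**The case against.** The strongest reply is that the primary contrast is between intervention and control conditions, and patients appear to go through both. For that within-patient contrast the gain is 0 to about 7%, so the larger savings belong to comparisons that the plan does not call primary. This stands, and it limits the point to between-group comparisons.

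An unadjusted t test is also valid, and these tests run only after a significant ANOVA. That stands too. The power figures are unconditional, and they rest on a back-solved SD for the CRDQ score, not a subscale SD. They show scale only; the variance ratios do not share this weakness.

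The plan may already hold an equivalent. If the repeated measures models code one shared baseline level, they are common-baseline models. The coding is not stated, and even on that reading the t tests and the regression list are unchanged.

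For the regression, the outcome is not pinned down as CRDQ or steps, or as a level or a change, and the assumed partial correlations have no source in the documents. This weakens the size, not the omission: a change score subtracts baseline but does not adjust for it. Dyspnea is listed and may carry part of the information, so the gain may be at the low end. Nothing says it is the CRDQ dyspnea dimension, and it would not cover the other three.

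Finally, independent-samples tests also ignore pairing if each patient contributes both conditions. That is a separate matter, which ANCOVA alone would not settle.

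**Conclusion.** The point holds. Baseline CRDQ is planned for every patient, yet the post hoc subscale tests cannot use it as a covariate and the regression's adjustment list leaves it out. Against whichever t test is better, baseline adjustment saves 9 to 25% of the variance for r between 0.3 and 0.7, with the largest saving at 0.5. It also removes the unspecified choice between final and change scores.

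The regression saving of 4 to 25% is less certain because it rests on assumed partial correlations. All these figures depend on assumed correlations and apply only to between-group comparisons. The readable text does not describe how the two halves are formed, and the ANCOVA advantage is cleanest under random allocation. No bias is shown and no planned test is invalid. This is an improvement in precision at no cost, of moderate importance.

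**What to change.** In the Analysis Plan:

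1. Add baseline CRDQ to the regression's adjustment variables wherever the comparison is between groups, using the baseline of the score being analysed.
2. Replace the post hoc independent-samples subscale t tests with ANCOVA, or a mixed model, adjusted for the same subscale's baseline value. A repeated-measures model with a common baseline mean is an acceptable equivalent; if that is the intention, state the coding.

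The cost is analysis-plan wording only. The baseline questionnaire is already scheduled for every patient, so no new data, visits or patients are needed.

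### The post hoc independent-samples t tests on the CRDQ subscales do not use the pairing that the two-period design provides

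*Combined protocol and SAP*

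**What the plan says.** The Study Protocol section puts each patient through both conditions. On the intervention side, for the eight-week "period each subject will receive weekly health coaching plus activity monitoring". On the control side, "During the last week of the control period all participants will be asked to wear the SenseWear Pro Armband for four days". The order differs between two halves of the sample: "During week 9 all participants (half of whom will be in the intervention period and half in the control period") repeat the CRDQ, and everyone completes it again at the end of week 17. A completer therefore supplies a baseline score, one intervention score and one control score.

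The Analysis Plan defines the primary outcomes as "change in daily steps and change in quality of life between the intervention and control conditions" and compares "quality of life measured by the CRDQ (baseline versus intervention versus control period"). It names two methods that respect repeated values on one patient: models for "trajectories from weeks 1, 9, and 17 using repeated measures models", and a multivariate repeated-measures ANOVA. If that ANOVA is significant at the 5% level, "post hoc independent-samples t tests will be conducted on the subscales of CRDQ". The two sets of scores that enter these t tests are not identified.

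A separate sentence adds that "Regression equations and correlations will be performed to determine the impact of the system/coaching and adherence on outcomes", adjusted for age, dyspnea, lung function, exacerbations and comorbidity. It does not say whether a patient contributes one row or several.

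**The concern.** The stated contrast is by condition, and the two condition scores come from the same people. An independent-samples t test of one against the other uses a standard error that includes between-patient variation, although that variation cancels within a patient. When the two scores are positively correlated, this standard error is too large.

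The subscale results are what a reader would use to see which CRDQ dimensions respond to coaching. An overall test that accounts for the pairing could be significant and then be followed by subscale tests that miss a moderate effect, for no reason other than the choice of test.

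**Working it through.** **Inputs.** From the Sample Size section: 104 patients, 52 per group, a CRDQ difference of 0.5 and 80% power. From the Analysis Plan: the 5% level. Assumed: a two-sided test, and a within-patient correlation r of 0.3, 0.5 or 0.7, because the text gives no value. The 0.25-point difference used below is illustrative and does not come from the plan.

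**The plan's own figure.** The text states no SD (Figures 11 and 12 are not shown), so 104 cannot be reproduced independently. It can be inverted. A two-group t test with 52 per group, two-sided 5% and 80% power detects a standardised difference of 0.5547, so SD = 0.5/0.5547 = 0.90. The normal approximation gives 0.91. I use 0.90 and apply it to the subscales as an assumption, since no subscale SD is given.

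**Standard errors, intervention against control, 104 patients.**
- Independent-samples: SD × √(2/104) = 0.90 × 0.1387 = 0.1248.
- Correct for paired data: SD × √(2(1−r)/104).
- Ratio: 1/√(1−r).

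**Actual two-sided error of the nominal 5% unpaired test:** 2 × [1 − Φ(1.96/√(1−r))].

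**Power** for a true difference δ (normal approximation):
- Unpaired: Φ[(δ − 1.96 × 0.1248)/SE_paired], where 1.96 × 0.1248 = 0.2446.
- Paired: Φ[δ/SE_paired − 1.96].

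| r | Paired SE | Ratio | Actual error | Power at 0.5, unpaired | Power at 0.5, paired | Power at 0.25, unpaired | Power at 0.25, paired |
|---|---|---|---|---|---|---|---|
| 0.3 | 0.1044 | 1.20 | 1.9% | 99.3% | 99.8% | 52% | 67% |
| 0.5 | 0.0883 | 1.41 | 0.6% | 99.8% | >99.9% | 52% | 81% |
| 0.7 | 0.0684 | 1.83 | 0.03% | >99.9% | >99.9% | 53% | 96% |

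For example, at r = 0.5 and δ = 0.25 the unpaired argument is (0.25 − 0.2446)/0.0883 = 0.06, which gives 52%. The paired argument is 0.25/0.0883 − 1.96 = 0.87, which gives 81%. With SD 0.91 the last two columns become 51-52% and 66%, 80% and 95%.

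**Simulation check** (20,000 runs under no effect, r = 0.5 and 0.7). The unpaired test by condition rejects in 0.5% and 0.05% of runs, and the paired test in 4.9% and 4.9%. An independent-samples test between order groups at week 9 rejects in 4.9% and 4.7%. An independent-samples test on within-patient period differences between order groups rejects in 4.9% and 4.9%.

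**The week-9 reading.** With 52 per order group, SE = 0.90 × √(2/52) = 0.1765. Power at 0.5 is Φ(0.5/0.1765 − 1.96) = Φ(0.87), about 81%, against more than 99% with both periods. At 0.25 it is Φ(0.25/0.1765 − 1.96) = Φ(−0.54), about 29%.

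**The proposed test has the paired precision.** A patient's week-9 minus week-17 difference has variance 2·SD²(1−r). The difference between the two order-group means has variance 2 × 2·SD²(1−r)/52. The condition effect enters that difference twice, with opposite signs in the two groups, so the estimate is half of it. Its variance is SD²(1−r)/52 = 2·SD²(1−r)/104, the square of the paired standard error above. A period effect common to both groups cancels.

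**The case against.** Four points can be made for the plan, and much of each stands.

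1. *The main analyses are already repeated-measures methods.* This is true. A reader might infer that the trial's whole efficacy analysis ignores pairing. The documents do not support that: the t tests are post hoc, run only after a significant repeated-measures ANOVA, and cover only the CRDQ subscales.

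2. *The t tests may be meant between the two order groups.* This is plausible: the ANOVA covers effects between as well as within groups, and the sample size is stated per group. At a single visit such a test is valid. But the plan does not say this is intended and its stated contrast is by condition. A week-9 comparison also leaves out every patient's second period.

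3. *The error is conservative and harmless at the target difference.* This is correct. The unpaired test by condition cannot inflate false claims of benefit when the correlation is positive, and at 0.5 points it still has over 99% power under these assumptions. The loss appears at smaller subscale effects.

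4. *The regressions are not shown to be wrong.* A reader might infer that they pool two rows per patient as independent, which at r = 0.3, 0.5 or 0.7 would give false-positive rates of 8.6%, 11.0% or 13.3% for patient-level terms (2 × [1 − Φ(1.96/√(1+r))]). The documents do not support that inference. They give no model form or unit of analysis. Age, lung function and comorbidity enter as adjustment variables, not as effects to be reported. Adherence to a programme that exists only in the intervention period fits naturally with one row per patient. What remains is missing detail.

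**Conclusion.** The point holds for the post hoc subscale tests. Used by condition, the named test gives intervals about 20% to 83% too wide and an actual error between 1.9% and 0.03%. At 0.25 points its power is about 52-53%, where a paired analysis has 67% to 96%. Used between order groups at week 9, it is valid but has about 81% power at 0.5 points instead of more than 99%. A within-patient test is better on either reading.

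These sizes rest on the assumed correlations, on 104 completers with both scores, on a back-solved SD carried over to the subscales, and on an illustrative 0.25-point effect. The contrasts that use both periods also assume that no intervention effect carries over into a later control period; that is a separate question.

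The consequence is limited: conservative follow-up tests, with almost no power lost at the plan's own meaningful difference. The overall test is not affected, and no fault in the regressions is established.

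**What to change.** In the Analysis Plan, replace the post hoc test with one of the following:
- For each CRDQ subscale, take every patient's week-9 minus week-17 difference and compare it between the two order groups with a t test. Report half the difference between the group means as the condition effect.
- Alternatively, report the condition contrast from a mixed model with a patient random intercept and a period term.

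If a week-9 comparison of the order groups is what is meant, say so and keep it as a supporting analysis.

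As a clarification only, state the unit of analysis for the regressions and correlations: a patient random intercept wherever both periods enter a regression, and one row per patient for correlations.

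The cost is a few sentences of wording and standard software. No additional patients, visits or data are needed.
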